Cover page study protocol

Study Title: Application of transcranial magnetic stimulation treatment in patients with oncological neuropathic pain to evaluate effectiveness on pain and quality of life

NCT number: 05480410

Date of the document: 1/02/2022

Study protocol

The protocol will be structured according to the national institute of health, the statements described by the clinical trial database and the SPIRIT declaration, which include detailed study description and design, intervention, outcome measures and individual participant data and results sharing statement.

10 patients will receive 20 sessions of transcranial magnetic stimulation using the MagVenture Mag Pro R20 device. These sessions will be conducted daily from Monday to Friday, lasting 20 minutes each, at an intensity of 81% with a motor threshold of 90 A/ns.

A pre-post design without a control group will be used to evaluate 2 elements: pain and quality of life.

The evaluation moments will be as follows:

- Pretest: Quality of life and pain will be assessed using the Visual Analog Scale (VAS) and the Brief Pain Inventory (BPI).

- Each session: Pain will be assessed using the VAS.

- Each week: Pain will be assessed using the BPI.

- Immediate Posttest: Quality of life and pain will be assessed using both scales.

- Posttest at 1 month and 3 months: Quality of life and pain will be assessed using both scales.

The patients will meet the following inclusion criteria: female or males aged over 18 and under 75 years, any stage of cancer, chemotherapeutic treatment consisting of taxanos or oxaliplatin, neuropathic pain with a minimum grade 2 severity based on the National Cancer Institute Common Terminology Criteria for Adverse Events scale (NCI-CTCAE, version 5.0), and a mean 2 score or above in a visual analogue scale (VAS) of pain. We will exclude patients with any psychiatric disorder including major depression; history of seizure, epilepsy, stroke and intracranial metallic devices. Patients should agree to avoid any extra use of medication or to make any changes to their pharmacological plan during the trial.

The aim of collecting these variables is to gather data and conduct statistical analysis to evaluate the effectiveness of transcranial magnetic stimulation on pain and quality of life in patients with neuropathic pain secondary to oncological treatment.

TEST 1: Pain

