This symptom will be evaluated using the Visual Analog Scale for pain and the Brief Pain Inventory (BPI), questionnaires that have been previously used in oncology populations (Goto et al., 2020; Khedr et al., 2015).

The Visual Analog Scale is rated from 0 to 10, where 0 indicates no pain and 10 represents the maximum pain.

The Brief Pain Inventory allows patients to rate the severity of their pain and the extent to which their pain interferes with their functionality.

An average is calculated for the elements that compose the pain severity category (worst pain, least pain, average pain, and current pain) and the elements that compose the pain interference category in functionality (interference in mood, walking, working, social interactions, sleeping, and enjoyment of life). Higher averages indicate worse patient condition.

Test 2: Quality of Life

Quality of life will be assessed using the Functional Assessment of Cancer Therapy FACT-GOG-NTX 13 scale, which has been psychometrically analyzed and validated in oncology populations (Cheng et al., 2020).

This scale includes 5 categories:

- Physical Well-being
- Social Well-being
- Emotional Well-being
- Functional Well-being
- Neurotoxicity

For scoring the scale, the ratings of these categories are summed, a higher total score means a better quality of life.

Determination of resting motor threshold

The target stimulation will be the primary motor cortex in its subdivision representing the hand; for this process, a basic trained operator identify the 'omega-shape' sulcus defining the Rolandic sulcus. Other authors have reported this specific hot spot target including the expert consensus established by a group of European experts, they described a Level A recommendation for the use of M1 as stimulation site for analgesic effect. Then the accurate position of the target will be adjusted according to the amplitude of the motor response on the contralateral hand, which a basic rTMS-trained physiotherapist will confirmed. This target has been shown in different investigations, to have greater specificity and effectiveness in the treatment of neuropathic pain. Once the target will be identified, it should be marked on a cap for the following sessions. A physiotherapist will be present weekly for assessment and to supervise patients' responses to treatment.

The occurrence of adverse events will be noted throughout the study period.

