Statistical Analysis Plan (SAP)

Study Title: Effectiveness of rTMS on Pain and Quality of Life in Patients With Cancer Neuropathic Pain

NCT Number: NCT05480410 **Version Date**: 5/06/2024

1. Objectives of the Statistical Analysis

The primary objective of the statistical analysis is to assess the effectiveness of transcranial magnetic stimulation (TMS) in reducing oncological neuropathic pain and improving quality of life in patients with cancer. This includes analyzing changes in Visual Analogue Scale (VAS), Brief Pain Inventory (BPI), and quality of life indicators (FACT-G and NTX subscales).

2. General Considerations

- All analyses will be conducted using IBM SPSS Statistics software (version specified in final results).
- A p-value < 0.05 will be considered statistically significant.
- No data imputation will be performed; all analyses will be based on observed values (complete case analysis).
- Assumptions required for each test (e.g., normality) will be tested and reported.

3. Descriptive Analyses

- Continuous variables (e.g., age, VAS scores, BPI scores) will be described using means, standard deviations, medians, ranges, and percentiles, depending on the distribution of the data.
- Categorical variables (e.g., sex) will be reported as frequencies and percentages.

4. Assessment of Normality

- The normality of continuous outcome variables will be tested using the **Shapiro-Wilk** test.
- If variables are not normally distributed, non-parametric methods will be used for inferential comparisons.

5. Inferential Analyses

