5.1. Within-Subject Comparisons

To evaluate the effectiveness of TMS over time:

- Wilcoxon signed-rank test will be used for paired comparisons of non-parametric variables between baseline and subsequent time points (e.g., Pre-VAS vs Day 5, Day 10, etc.).
- **Paired t-tests** will be used only if variables demonstrate normal distribution.

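### No stable analgesic regimen is required before the pretest and no medication record is described, so this uncontrolled study cannot separate a drug effect from a TMS effect in patients whose medication recently changed or changes on study

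*Protocol*

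**What the plan says.** The eligibility paragraph of the protocol ends with the sole provision on concomitant medication: "Patients should agree to avoid any extra use of medication or to make any changes to their pharmacological plan during the trial". The inclusion and exclusion criteria themselves cover age, cancer stage, type of chemotherapy, neuropathy grade, a minimum VAS score, and psychiatric and neurological history. None sets a period of unchanged analgesic treatment before the pretest, and no run-in is described.

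On design: "A pre-post design without a control group will be used to evaluate 2 elements: pain and quality of life". Follow-up extends beyond treatment: "Posttest at 1 month and 3 months: Quality of life and pain will be assessed using both scales".

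Two provisions at the end of the protocol could bring a medication change to light: "A physiotherapist will be present weekly for assessment", and "The occurrence of adverse events will be noted throughout the study period". Neither is described as capturing drugs, doses or dates.

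The SAP does not mention medication. Section 2 states: "No data imputation will be performed; all analyses will be based on observed values (complete case analysis". Section 5.1 states that the "Wilcoxon signed-rank test will be used for paired comparisons of non-parametric variables between baseline and subsequent time points", with paired t-tests if the data are normal, and presents these comparisons as the evaluation of TMS effectiveness. Section 5.2 adds repeated measures ANOVA. Section 6 allows optional covariate adjustment, with age, sex and baseline pain as examples.

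**The concern.** In a single-arm study the within-patient change is the only evidence of effect. No comparison group shares a drug effect and cancels it. Two gaps follow.

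- **Before the pretest.** A patient whose analgesic was started or raised shortly before the pretest is eligible and complies fully with the no-change rule. Any gain still developing falls inside the pre-post change and makes TMS look better. A drug already at full effect does no harm, because it is part of the baseline.
- **After the pretest.** Patients with persisting pain may add analgesics, which inflates the apparent benefit. Responders may cut down, which hides it. With no described record, the report could not say which happened, when, or in how many of the 10 patients.

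The SAP has no rule for a score taken after a medication change. Such a score enters every analysis as an ordinary observed value.

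**Working it through.** There is no plan figure to reproduce: the sample of 10 comes without an effect size, SD or power. The check is an illustration of size.

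**Inputs from the documents.** n = 10; significance at 0.05 (SAP section 2; taken as two-sided, since sidedness is not stated); paired Wilcoxon or t-test against baseline (section 5.1); Greenhouse-Geisser or Huynh-Feldt correction only when Mauchly's test shows a violation (section 5.2). For VAS bounds, "The Visual Analog Scale is rated from 0 to 10".

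**Inputs assumed.** True TMS effect 0; k = 1 or 2 patients affected; drug effect d = 2 to 3 VAS points; SD of the paired change 1.5 to 2.0. The documents give none of these.

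**Step 1, shift in mean change.** Shift = k × d / n.
- k = 2: 2 × 2 / 10 = 0.4 to 2 × 3 / 10 = 0.6 points.
- k = 1: 1 × 2 / 10 = 0.2 to 1 × 3 / 10 = 0.3 points.

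**Step 2, chance of a significant decrease in one section 5.1 comparison.** Ten normal changes with mean 0, d subtracted from k of them; exact Wilcoxon (lower critical value 8 at n = 10) and paired t; 100,000 simulated trials; favourable tail only.

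| Patients affected | SD 2.0, d = 2 | SD 2.0, d = 3 | SD 1.5, d = 2 | SD 1.5, d = 3 |
|---|---|---|---|---|
| 2 of 10, Wilcoxon | 6.0% | 7.6% | 7.2% | 8.8% |
| 2 of 10, paired t | 6.2% | 7.7% | 7.2% | 8.6% |

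With nobody affected the rate is 2.3-2.5%. With 1 of 10 affected it is 3.9-4.7% (Wilcoxon) or 4.0-4.4% (t).

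**Step 3, scale limits.** Holding post-treatment scores within 0 to 10 reduces the shift for k = 2 to 0.37-0.55 points (baselines spread evenly over 2 to 9) or 0.33-0.47 (baselines 2 to 4). The chance stays at about 6-9%.

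**Step 4, opposite changes.** If 2 patients fall by d and 1 other, having reduced analgesics, rises by d, the Wilcoxon figure is 1.3-2.6%, at or below the rate with no drug effect. The net direction depends on facts that only a record would supply.

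**Step 5, section 5.2 ANOVA.** Assume seven VAS occasions (pretest, days 5, 10, 15 and 20, 1 and 3 months), independent errors of SD/√2 per reading, and Greenhouse-Geisser applied only when Mauchly's test rejects. With no drug effect the rejection rate is about 5%. With 2 of 10 affected, the drug effect either rising through treatment or present only at 1 and 3 months, it is 6-10%. This F test is non-directional, so its 5% starting point should not be set against the one-tail 2.5% of step 2. The figures do not show that either analysis is the better protected.

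**The case against.** **The protocol already addresses medication.** It bars both extra use and changes to the plan while the patient is in the trial. That stands, and it lowers the risk. A reader might infer that medication is uncontrolled here, which the text does not support. What remains is patients whose regimen changed just before the pretest, whom the rule does not reach, and breaches, which nothing described would document.

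**The effect is small and the frequency unknown.** This stands. A reader might go further and infer that drug effects could account for most of a positive result. If all ten patients drifted by 0.5 to 1.0 SD, the paired t-test would be significant 29-80% of the time, but nothing in the documents suggests drift in every patient.

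**The direction is not fixed.** This also stands. A reader might infer that any unrecorded change flatters TMS; step 4 shows otherwise. Only the effect still developing at the pretest has a clear direction.

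**The study is exploratory and the missing control group matters more.** SAP section 7 does promise cautious interpretation, and a medication record cannot replace a control arm. Caution in wording, however, does not tell the reader whether any patient's medication changed. Section 6 leaves its list of confounders open, but a variable that was not recorded cannot be adjusted for.

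**A record may exist at the site.** It may; the protocol is a short outline. The point is confined to what the two documents describe. If a record exists, what is left is the reporting step and, for future enrolment, the stability criterion.

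**Conclusion.** Both absences hold in the text. Following the eligibility rule exactly still admits a patient whose drug effect is developing, and section 5.1 would then count that effect as TMS effectiveness. An unrecorded change on study could push the result either way.

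The size is modest: a mean shift of 0.4 to 0.6 VAS points before scale limits, and a 6-9% rather than about 2.5% chance of a spurious significant decrease in one paired comparison, if 2 of 10 patients are affected. The breach rate, drug effect, SD of change and baseline distribution are all assumptions. The finding does not invalidate the planned analysis. It identifies one avoidable alternative explanation that the sponsor should remove because doing so is cheap.

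**What to change.** 1. **Eligibility.** Add an inclusion criterion that analgesic and neuropathic-pain treatment has been unchanged for a stated period before the pretest, for example 4 weeks (an assumed figure; the sponsor may set another). Enrolment status is not stated. If enrolment has closed, retrieve the date of the last change for each patient instead.
2. **Record.** Keep the no-change rule as written. At the pretest, weekly, immediate, 1-month and 3-month assessments, record analgesic and neuropathic-pain drugs, doses, dates of change, and any breach or clinically needed extra use.
3. **Reporting.** Keep the observed-value analysis as the main one. Beside it, report how many patients changed medication, in which direction and when, with a descriptive count of patients who improved without an increase. A section 5.1 comparison leaving out readings after a recorded increase is optional and should carry the caveat that it may remove non-responders. None of this needs imputation.

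**Cost.** One eligibility line, one extra item at visits already planned, one supplementary table, and a short enrolment delay for patients with a recently changed regimen. The optional comparison has less power: with 2 patients left out and a true 2-point fall, Wilcoxon power drops from 79% to 61% (SD 2) or from 95% to 85% (SD 1.5), at the affected time points only. Placebo response and regression to the mean remain untouched.

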Statistical Analysis Plan (SAP)

Study Title: Effectiveness of rTMS on Pain and Quality of Life in Patients With Cancer Neuropathic Pain

NCT Number: NCT05480410 **Version Date**: 5/06/2024

1. Objectives of the Statistical Analysis

The primary objective of the statistical analysis is to assess the effectiveness of transcranial magnetic stimulation (TMS) in reducing oncological neuropathic pain and improving quality of life in patients with cancer. This includes analyzing changes in Visual Analogue Scale (VAS), Brief Pain Inventory (BPI), and quality of life indicators (FACT-G and NTX subscales).

2. General Considerations

- All analyses will be conducted using IBM SPSS Statistics software (version specified in final results).
- A p-value < 0.05 will be considered statistically significant.
- No data imputation will be performed; all analyses will be based on observed values (complete case analysis).
- Assumptions required for each test (e.g., normality) will be tested and reported.

3. Descriptive Analyses

- Continuous variables (e.g., age, VAS scores, BPI scores) will be described using means, standard deviations, medians, ranges, and percentiles, depending on the distribution of the data.
- Categorical variables (e.g., sex) will be reported as frequencies and percentages.

4. Assessment of Normality

- The normality of continuous outcome variables will be tested using the **Shapiro-Wilk** test.
- If variables are not normally distributed, non-parametric methods will be used for inferential comparisons.

5. Inferential Analyses

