5.2. Repeated Measures Analysis

- **Repeated measures ANOVA** will be conducted to evaluate the impact of the intervention over multiple time points for continuous outcome variables such as VAS, FACT-G, and TOI.
- When the sphericity assumption is violated (tested via **Mauchly's test**), Greenhouse-Geisser or Huynh-Feldt corrections will be applied.
- Effect sizes (partial eta squared) and observed power will be reported for all significant outcomes.

6. Multivariable Analysis

• If sample size allows, analysis of covariance (ANCOVA) or linear mixed models may be considered to adjust for potential confounders such as age, sex, and baseline pain level.

7. Handling of Multiple Comparisons

• Due to the exploratory nature of the study and small sample size, no formal adjustment for multiple comparisons will be applied. However, results will be interpreted with caution, and this limitation will be noted in the final report.

8. Subgroup Analyses

• No pre-specified subgroup analyses are planned due to limited sample size.

9. Deviations from Planned Analysis

• Any deviations from this pre-specified plan will be documented and justified in the final study report.

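### Complete-case repeated-measures ANOVA drops any of the 10 patients who misses one included time point; plan a mixed model on all observed values and list the time levels

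*SAP*

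**What the plan says.** SAP section 2 sets one missing-data rule for everything: "No data imputation will be performed; all analyses will be based on observed values (complete case analysis". Section 5.2 says that repeated-measures ANOVA "will be conducted to evaluate the impact of the intervention over multiple time points for continuous outcome variables such as VAS, FACT-G, and TOI". It lists no time levels. If Mauchly's test rejects sphericity, "Greenhouse-Geisser or Huynh-Feldt corrections will be applied".

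Section 5.1 plans paired tests "between baseline and subsequent time points (e.g., Pre-VAS vs Day 5, Day 10, etc", by Wilcoxon or, for normally distributed variables, by t-test. Section 6 mentions mixed models only as an option if the sample allows, and for a different purpose: "linear mixed models may be considered to adjust for potential confounders such as age, sex, and baseline pain level". Section 4 sends non-normal outcomes to non-parametric methods.

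The protocol plans 10 patients, no control group and 20 weekday sessions. Its list of evaluation moments puts quality of life at pretest, immediate posttest, 1 month and 3 months. VAS is collected far more often: "Each session: Pain will be assessed using the VAS".

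**The concern.** Standard repeated-measures ANOVA needs a full row per patient. Under the section 2 rule, one missed included visit removes the patient from that analysis. The plan gives no dropout allowance, minimum number of completers or missing-data sensitivity analysis, and section 6 does not fill the gap because its mixed models are for confounders.

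Two separate things are at stake. Scattered misses throw away collected ratings and precision. Dropout related to pain biases the change, and with no control arm the within-patient change is the only evidence of effect. The wording in section 2 also mixes observed values with complete cases, so it is unclear whether the paired tests use every patient with both visits or only patients with all visits.

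**Working it through.** The plan gives no missing rate, SD, correlation or sample-size calculation, so there is no figure of its own to reproduce.

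**Inputs.** From the protocol: n = 10; k = 4 quality-of-life moments; VAS at 20 sessions plus pretest, immediate posttest, 1 month and 3 months, so up to 24 moments. Assumed: k = 7 for VAS (pretest, Days 5, 10, 15 and 20, 1 and 3 months, extrapolated from the example in section 5.1); m = 5% or 10% missed independently at each post-baseline visit; baseline always observed.

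**Step 1: data lost to the ANOVA.** Expected complete patients = 10(1−m)^(k−1). Ratings collected = 10[1 + (k−1)(1−m)]. Ratings used = k × complete patients.

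| k | m | Complete patients | Collected | Used | Discarded |
|---|---|---|---|---|---|
| 4 | 5% | 10 × 0.95³ = 8.57 | 38.5 | 34.3 | 11% |
| 4 | 10% | 10 × 0.90³ = 7.29 | 37.0 | 29.2 | 21% |
| 7 | 5% | 10 × 0.95⁶ = 7.35 | 67.0 | 51.5 | 23% |
| 7 | 10% | 10 × 0.90⁶ = 5.31 | 64.0 | 37.2 | 42% |

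If all 24 VAS moments were entered, which section 5.2 does not exclude, expected completers would be 3.1 at 5% and 0.9 at 10%.

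**Step 2: the sphericity test.** Mauchly's test cannot be computed when complete patients are fewer than k. The binomial probability of that at 5% / 10% is 0.01% / 0.6% for k = 4 and 26% / 77% for k = 7. With 24 levels it is certain even without missing data, because 10 < 24. The SAP has no rule for this case.

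**Step 3: precision of the 3-month change, scattered misses.** Simulated with n = 10, six assumed correlation structures and 4,000 trials each, against a best-case estimator using all observed values with known covariance. Pair-by-pair deletion, as section 5.1 can be read, gives an SD larger by 0.6-1.7% at 5% missing and 1.9-4.6% at 10%, over both 4 and 7 levels. Listwise deletion gives 6-8% in the mildest setting (4 levels, 5%) and 38-42% in the heaviest (7 levels, 10%).

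**Step 4: bias if dropout follows worsening.** Simulated with SD 2, no true change, and monotone dropout whose hazard rises with the last rating minus baseline. With monotone dropout, the patients seen at 3 months are the complete patients, so the ANOVA and the 3-month paired test share the same bias. In large samples at 7 levels, the spurious 3-month VAS fall is 0.07-0.44 points at 28% loss and 0.02-0.16 at 10% loss. In trials of 10 patients at 28% loss (stronger dropout dependence only):

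| Levels | Complete-case bias | Mixed model, time-indexed serial correlation |
|---|---|---|
| 7 | −0.13 to −0.45 | −0.13 to +0.03 |
| 4 | −0.20 to −0.38 | −0.03 to +0.06 |

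The sampling SD of the change at n = 10 is 0.64-1.04 points in these runs.

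**Step 5: which covariance.** At 7 levels with 28% loss, when correlation decays with calendar time (with or without a constant share), overall type I error was 9.7-12.5% for AR(1) by visit order and 9.9-13.0% for a random intercept alone. Over all runs it was 3.4-5.9% for time-indexed serial correlation, 4.5-6.6% with a patient intercept added, and 1.0-5.2% for ANOVA always corrected by Greenhouse-Geisser. For the single 3-month contrast neither time-indexed version is best throughout. Serial alone falls to 0.4-1.1% if correlation never decays; with the intercept the rate can reach 8.9% if correlation follows visit order. A separate 400-trial check, with 5% missing and a true patient intercept plus serial decay, gave 2.2% for serial alone and 4.8% with the intercept.

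**The case against.** The strongest reply is that section 5.1, not 5.2, supplies the baseline-to-visit changes, and a paired test needs only two visits. This stands. A reader might infer from the listwise figures that the plan gives up around 40% in precision on the 3-month change. The documents do not support that: section 5.2 plans an overall test rather than a 3-month contrast, and pair-by-pair tests lose about 1-5%. Bias at visits that nobody misses is likewise confined to listwise deletion. Bias at 3 months is not; the paired test shares it.

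A reader might also add the two harms together. They come from different mechanisms. With monotone dropout the ratio of complete-case to mixed-model SD at 3 months was 0.93-1.07, so there is hardly any precision to regain, and bias needs informative dropout. The documents give no rate or direction, and dropout after improvement would reverse the sign.

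The largest losses rest on an assumed seven-level VAS set; only the four quality-of-life moments are fixed by the protocol. Type I error is no argument for the mixed model either, since always applying Greenhouse-Geisser already controls it.

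Finally, section 7 pleads "Due to the exploratory nature of the study and small sample size". That is its reason for not adjusting for multiplicity. It gives no reason to discard ratings already collected, least of all with 10 patients.

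**Conclusion.** The concern holds for the ANOVA in section 5.2, conditionally on missed visits. At 5-10% missed per visit it would discard 11-21% of quality-of-life ratings, and 23-42% of VAS ratings if seven levels are used. The paired tests lose little precision if run pair by pair, which section 2 leaves unclear. If dropout follows worsening, both methods show a false improvement at 3 months of about 0.1-0.45 VAS points at 28% loss and SD 2. That is modest beside the sampling error, so it would be wrong to infer that an observed improvement must be an artefact of dropout. With complete data nothing is lost. The missing rates, SD, correlations and dropout mechanism are all assumptions. The change is worth making because it is cheap, but it is not a fatal fault.

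**What to change.** 1. **SAP 2.** Replace the complete-case rule with use of all observed values, and state that each paired test in 5.1 uses every patient with both visits.
2. **SAP 5.2.** Make the planned longitudinal analysis a REML linear mixed model on all observed values, with categorical time, patient as subject, a small-sample df method such as Kenward-Roger, and one pre-specified parsimonious covariance that reflects the unequal visit spacing. One option is serial correlation indexed by actual days, with and without a patient intercept, naming one as primary and the other as sensitivity; the results above do not settle which. Keep repeated-measures ANOVA as a sensitivity analysis, always Greenhouse-Geisser corrected, without the Mauchly step.
3. **Time levels.** List them for each outcome, with a short set for VAS, and report patients and observations in every analysis.
4. **SAP 4.** Say how the mixed model fits the normality rule, for example by judging normality on residuals and keeping the Wilcoxon tests as the non-parametric check.

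**Cost.** SAP wording and a software check; no new data. Section 2 says "All analyses will be conducted using IBM SPSS Statistics software (version specified in final results", so the sponsor must confirm that the version used can fit the chosen covariance and df method, or name another package. A covariance structure has to be assumed with only 10 patients. Dropout bias is reduced only if dropout depends on observed ratings; even then, 0.13 points remained in the simulation where correlation followed visit order.
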